8.3. Adverse Events

The definitions and details on recording, evaluating, and reporting of AEs, SAEs, pIMDs, and also pregnancies are provided in Appendix 4.

The investigator and any designees are responsible for detecting, documenting, and recording events that meet the definition of an AE or SAE and remain responsible for following up AEs that are serious, considered related to the study intervention or study procedures, or that caused the participant to discontinue the study/study intervention (see Section 7).

8.3.1. Time Period and Frequency for Collecting AEs/SAEs, pIMDs, and Pregnancy Information

Collection of AEs, SAEs, pregnancies, and pIMDs will be performed at the time points and periods specified in Table 15.

Medical occurrences that begin before the start of study intervention but after obtaining informed consent will be recorded on the medical history section of the eCRF, not the AE section.

All SAEs will be recorded and reported to IQVIA within 24 hours. The investigator will submit any updated SAE data to IQVIA within 24 hours of it being available through the Expedited Report Form.

Investigators are not obligated to actively seek AE or SAE after the participant concluded the study participation. However, if the investigator learns of any SAE, including a death, at any time after the participant has been discharged from the study, and the event is considered reasonably related to the study intervention, the investigator must notify IQVIA.

Table 15 Time Period and Frequency for Collecting AE/SAE and Pregnancy Information

	Visit 1	Visit 2		Visit 3		Visit 4	Visit 5		Visit 6	Visit 7
	Day 1	Day 7		Month 2		Month 3	Month 6		Month 7	Month 12
Event	Dose 1	7 days post- Dose 1	28 days post- Dose 1	Dose 2	7 days post- Dose 2	28 days post- Dose 2	Dose 3	7 days post- Dose 3	28 days post- Dose 3	Study conclusion
Administration site and systemic solicited events										
Unsolicited AEs										
SAEs (all, fatal, related)										
pIMDs										
AEs/SAEs leading to withdrawal from the study										
SAEs related to study participation or concurrent GSK										
medication/vaccine Pregnancies/pregnancy outcomes										

AE = adverse event; SAE = serious adverse event; pIMD = potentially immune-mediated disease

8.3.2. Method of Detecting AEs and SAEs, Pregnancies, and pIMDs

Care will be taken not to introduce bias when detecting AEs and/or SAEs. Open-ended and non-leading verbal questioning of the participant is the preferred method to inquire about AE occurrences. Memory aids used by participant/participant's parent(s)/LAR(s), will be reviewed for health-related issues of participants and for potential AEs, which will be transcribed in eCRFs.

8.3.3. Clinically Significant Abnormal Laboratory Findings

The investigator must record any clinically relevant changes occurring during the study in the AE section of the eCRF. All clinically significant abnormal laboratory test values should be repeated until the values return to normal/baseline, or until they are no longer considered significantly abnormal by the investigator. If such values do not return to normal/baseline after an interval judged reasonable by the investigator, the etiology of the abnormal value should be identified, and the sponsor notified. In any case, the investigator should document they reviewed the laboratory report.

8.3.4. Follow-up of AEs and SAEs, Pregnancies, and pIMDs

After the initial AE/SAE/pIMD, or pregnancy report, the investigator is required to proactively follow each participant at subsequent visits/contacts. All SAEs and pIMDs will be followed until resolution, stabilization, the event is otherwise explained, or the participant is lost to follow-up.

8.3.5. Regulatory Reporting Requirements for SAEs, Pregnancies, and pIMDs

Once an investigator becomes aware that a study participant has experienced SAE, pIMD, or pregnancy during the study, they or designated study staff must report it to IQVIA within the timeframes provided in Table 16 via an electronic Expedited AE Report or Expedited Pregnancy Report. If the complications fulfill serious criteria, an SAE report should additionally be completed within 24 hours. This is essential for meeting legal obligations and ethical responsibilities for participant safety and the safety of a study intervention under clinical investigation.

For SAEs/pIMDs, the investigator will always provide an assessment of causality at the time of the initial report.

Follow-up of relevant information on a pregnancy should be submitted the same way within 2 weeks once this information becomes available. Pregnancy outcome should be reported within 2 weeks.

Local regulatory requirements and GSK's policy for the preparation of an investigator safety report for Suspected Unexpected Serious Adverse Reactions must be followed. These reports will be forwarded to investigators as necessary.

GSK/IQVIA has a legal responsibility to notify local authorities and other regulatory agencies about the safety of a study intervention under clinical investigation. GSK/IQVIA will comply with country-specific regulatory requirements related to safety reporting to the regulatory authority, IRB/IEC, and investigators.

Table 16 Expedited Reporting of SAEs, Pregnancies, and pIMDs

Type of Event	Initial Repor	ts	Follow-up of Relevant Information on a Previous Report			
	Timeframe	Documents	Timeframe	Documents		
SAE	24 hours ^{1,2,3}	electronic Expedited AE Report	24 hours ¹	electronic Expedited AE Report		
Pregnancy	2 weeks ¹	electronic Pregnancy Report	2 weeks	electronic Pregnancy Report		
pIMD	24 hours ^{2,4}	electronic Expedited AE Report	24 hours ¹	electronic Expedited AE Report		

AE = adverse event; pIMD = potentially immune-mediated disease; SAE = serious adverse event

8.3.6. Treatment of Adverse Events

Any medication administered for the treatment of an AE should be recorded in the Expedited AE Report of the participant's eCRF.

8.3.7. Participant Card

The investigator or investigator's designee must provide the participant/participant's parent(s)/LAR(s) with a "participant card" containing information about the clinical study. The participant/participant's parent(s)/LAR(s) must be instructed to keep the participant card in her/their possession at all times throughout the study. In an emergency, this card serves to inform the responsible attending physician/LAR/caregiver/family member that the participant is in a clinical study and that relevant information may be obtained by contacting the investigator or his/her back-up.

8.3.8. Medical Device Deficiencies

This clinical study will collect information of any device deficiencies associated with the study interventions that are combination products. Refer to Glossary of Terms for the definition of a combination product and a medical device deficiency.

¹ Timeframe allowed after receipt or awareness of the information by the investigator/study center staff.

² The investigator will confirm review of the SAE/pIMD causality by ticking the "reviewed" box in the electronic Expedited AE Report within 72 hours of submission of the SAE/pIMD.

³ For coronavirus disease 2019 (COVID-19) related SAEs, reports should be submitted following routine procedures for SAEs.

⁴ Timeframe allowed once the investigator determines that the event meets the protocol definition of an pIMD.

8.3.8.1. Detection, Follow-up, and Reporting of Medical Device Deficiencies

The investigator is responsible for the detection, documentation and prompt reporting of any medical device deficiency occurring during the study to IQVIA. Device deficiencies should be reported within 24 hours after the investigator determines that the event meets the protocol definition of a device deficiency. New or updated information will be recorded on the originally completed form with all changes signed and dated by the investigator and reported to IQVIA within 24 hours.

Refer to Appendix 4 for details on recording and reporting of medical device deficiencies.

The investigator will ensure to follow the participants with reported device deficiencies and perform any additional investigations to determine the nature and/or causality of the deficiency.

8.3.8.2. Regulatory Reporting of Medical Device Deficiency When Used as Combination Product

The investigator will promptly report all device deficiencies occurring with any medical device provided for use in the study in order for IQVIA to fulfill the legal responsibility to notify appropriate regulatory authorities and other entities about certain safety information relating to medical devices being used in clinical studies. Refer to Appendix 4 for details of reporting.

The investigator, or responsible person according to local requirements (e.g., the head of the medical institution), will comply with the applicable local regulatory requirements relating to the reporting of device deficiencies to the IRB/IEC.

8.4. Study Procedures During Special Circumstances

During special circumstances (e.g., COVID-19 pandemic), the specific guidance from local public health and other competent authorities regarding the protection of individuals' welfare must be followed. For the duration of such special circumstances, the following measures may be implemented for enrolled participants:

- Safety follow-up may be made by a phone call, other means of virtual contact, or home visit, if appropriate.
- If the eDiary device was provided to the participant/participant's parent(s)/LAR(s), it may be returned to the study center by conventional mail after the end of the relevant data collection period. If the application (app) was provided to the participants' parent(s)/LAR(s) for use on their personal device, the app can be disabled remotely.
- Biological samples may be collected at a different location* other than the study center or at participant's home. Biological samples should not be collected if they cannot be processed in a timely manner or appropriately stored until the intended use.

*Note: It is the investigator's responsibility to identify an alternate location. The investigator should ensure that this alternate location meets ICH Good Clinical Practice (GCP) requirements, such as adequate facilities to perform study procedures, appropriate training of the staff, and documented delegation of responsibilities in this location. This alternate location may need to be covered by proper insurance for the conduct of study on participants by investigator and study center staff other than the designated study center.

Any impact of the above-mentioned measures on the study data analysis and results will be determined on a case-by-case basis and reported upon the study completion.

The impact on the Per Protocol Set (PPS) for immunogenicity will be determined on a case-by-case basis. Any impact of the above-mentioned measures on the study results will be described in the Clinical Study Report.

9. STATISTICAL CONSIDERATIONS

9.1. Statistical Hypotheses

The primary objective of the study will be evaluated descriptively.

In this study, exploratory immunologic non-inferiority analyses will be performed, to help in decision making of the formulation selection for phase 3.

9.2. Sample Size Determination

The target enrollment is 1080 participants (270 participants in each group).

The enrollment to the study will be performed in 2 steps. In Step 1, 48 participants (12 per group) will be enrolled and vaccinated. If no safety concern is identified, the remaining 1032 participants will be enrolled and vaccinated in Step 2 to reach 1080 participants.

9.2.1. Statistical Considerations on Safety Assessment

In Step 1, the sample size of 12 participants per group would provide a probability of at least 80% to observe at least 1 AE, if the true AE rate is equal to or greater than 12.6%.

The sample size of 270 participants per group would provide a probability of at least 93% to observe at least 1 Grade 3 AE, if the true Grade 3 AE rate is equal to or greater than 1.0%.

Table 17 provides the 2-sided 95% exact confidence interval (CI) for a range of AE rates (270 participants per group).

Table 17 2-sided 95% Exact Confidence Intervals for the True Adverse Event Rate for Various Observed Adverse Event Rates (270 Participants per Group)

	Observed number	Observed	2-sided 95% exact confidence interval			
Participants vaccinated	participants reporting the adverse events	percentage of participants with the adverse events	Lower limit	Upper limit		
	0	0.0	0.0%	1.4%		
	1	0.4	0.0%	2.0%		
	10	3.7	1.8%	6.7%		
270	27	10.0	6.7%	14.2%		
270	30	11.1	7.6%	15.5%		
	50 18.5		14.1%	23.7%		
	100	37.0	31.3%	43.1%		
	150	55.6	49.4%	61.6%		

If the true Grade 3 AE rate is 10%, with the sample size of 270 participants per group, the incidence of Grade 3 AEs above 14.2% with 97.5% confidence (14.2%=upper limit for 2-sided 95% CI) will be ruled out.

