- Each holding rule 2a-2c has more than 89% chance of not being met for vaccination with a true incidence rate below 10% and more than 60% chance of being met for vaccination with a true incidence rate above 25%.

[figure not shown]

Figure 2 Probability of Not Meeting Holding Rules 1 and 2 for 12 Participants per Study Group in Step 1

8.2.3.3. iSRC Evaluation

The iSRC will review the accumulated safety data up to 7 days post-dose 1 of sentinel participants in Step 1*. The iSRC will have access to the participant randomization list and will review unblinded data. The iSRC members will determine whether any of the pre-defined holding rules are met (refer to Section 8.2.3) or if there is any other safety signal. If no safety signal is observed, vaccination of the "Step 1" participants will continue, and vaccination of the remaining participants ("Step 2" participants) will be initiated.

Following this initial review(s), the iSRC will review all available safety data on a regular basis (monthly) until data from 1-month post-dose 2 for all participants and data from 1-month post-dose 3 for Step 1 participants are reviewed. During these reviews, monitoring of safety events will be done with no holding rules assessment (refer to the iSRC charter for details). It will be up to iSRC to trigger a study hold or study change if deemed necessary. In addition to the iSRC, the project SRT will review blinded data on a regular basis throughout the study.

*In case not all 48 of the Step 1 participants are enrolled and vaccinated with a first dose of study vaccine by 30 September 2022, the iSRC will review the accumulated safety data up to 7 days post-dose 1 of all participants available by that date. If no safety signal is identified, these participants will be vaccinated with a second dose. To avoid any additional participants running out of the allowed interval range for their second vaccine dose, additional iSRC review(s) may need to be planned to review the safety data up to 7 days post-dose 1 of these participants, but

only when all 48 Step 1 participants have been enrolled and their data have been reviewed by the iSRC, the iSRC will decide on the initiation of the vaccination of Step 2 participants.

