9.4.1. Primary Endpoints Analyses

9.4.1.1. Analysis Related to Safety and Reactogenicity

The safety analysis will be based on the Exposed Set (ES).

The percentage of participants reporting each solicited administration site event and systemic event assessed as Grade 3 in intensity during the solicited follow-up period (Day 1 – Day 7 after vaccine administration) will be tabulated, per dose and over the whole vaccination course, with exact 95% CI.

The percentage of participants with at least 1 report of unsolicited AE assessed as Grade 3 in intensity classified by the Medical Dictionary for Regulatory Activities (MedDRA) reported up to 28 days after vaccination will be tabulated with exact 95% CI.

The percentage of participants with at least 1 report of a SAEs classified by MedDRA from first vaccination up to Month 12, will be tabulated with exact 95% CI.

The percentage of participants in Step 1 outside the defined normal ranges for each biochemical and hematological parameter measured in the study at Day 7 post-dose 1 will be tabulated with exact 95% CI.

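### Protocol 9.2.1 attaches the exact upper limit for an observed 27/270 (14.2%) to a true Grade 3 AE rate of 10% and presents the exclusion of higher rates as certain; it happens in about 55% of trials per group

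*Protocol*

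**What the plan says.** Section 9.2 of the protocol sets the size: "The target enrollment is 1080 participants (270 participants in each group"). Section 9.2.1 then describes what that size delivers for safety. Table 17 lists, in the words of its title, "Exact Confidence Intervals for the True Adverse Event Rate for Various Observed Adverse Event Rates (270 Participants per Group"); the row for 27 events in 270 (10.0%) shows limits of 6.7% and 14.2%.

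The sentence after the table reads "If the true Grade 3 AE rate is 10%, with the sample size of 270 participants per group", and goes on to say that an incidence of Grade 3 events above "14.2% with 97.5% confidence (14.2%=upper limit for 2-sided 95% CI) will be ruled out".

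Elsewhere the protocol attaches a probability when it assumes a true rate. The same section gives at least 80% for seeing one or more AEs among 12 participants at a true rate of 12.6% or more. For 270 participants it gives "a probability of at least 93% to observe at least 1 Grade 3 AE, if the true Grade 3 AE rate" is 1.0% or more. Section 8.2.3.2 also quotes a probability for holding rules 2a-2c at true rates below 10%.

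Nothing else in the protocol or the SAP restates or corrects the sentence.

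**The concern.** An exact confidence limit is a function of the observed count. Fixing the observed count at 27 fixes the limit at 14.2%. Fixing the true rate at 10% does not: the count is then binomial with mean 27, and the limit moves with it. The sentence carries the limit from the first situation into the second and states a random outcome as if it were assured.

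The reference to 97.5% confidence does not repair this. That figure says how improbable 27 or fewer events would be if the true rate were 14.2%. It does not say how probable 27 or fewer events are if the true rate is 10%.

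This is the only statement in 9.2.1 of which upper bound on the Grade 3 rate 270 participants per group can exclude, and Grade 3 events are among the primary safety endpoints. A reader planning around it would take exclusion of rates above 14.2% as guaranteed at a true 10%, when the odds are close to even.

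**Working it through.** **Inputs.** n = 270 per group (protocol 9.2); true Grade 3 rate 10% and bound 14.2% (9.2.1, sentence after Table 17); two-sided 95% exact limits (Table 17).

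**Step 1: reproduce the protocol's figure.** The Clopper-Pearson upper limit for x events in n is the 0.975 quantile of Beta(x + 1, n − x).

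| Events of 270 | Exact upper limit |
|---|---|
| 26 | 13.791% |
| 27 | 14.215% |
| 28 | 14.639% |

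For 27 events the full interval is 6.694% to 14.215%, which matches the printed 6.7% to 14.2%. All eight rows of Table 17 reproduce to one decimal. The two neighbouring probabilities in 9.2.1 also reproduce: 1 − (1 − 0.126)^12 = 0.801 and 1 − 0.99^270 = 0.934.

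**Step 2: the probability that the sentence leaves out.** The upper limit is at or below the 27-event value only if 27 or fewer events are observed. With X ~ Binomial(270, 0.10):

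- P(X ≤ 27) = 0.551
- P(X ≥ 28) = 1 − 0.551 = 0.449, in which case the upper limit is at least 14.639%

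**Step 3: what the 97.5% refers to.** With X ~ Binomial(270, 0.14215), P(X ≤ 27) = 0.025. This is the tail at the limit, and its complement is the 97.5%. It is a different quantity from the 0.551 in step 2.

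**Step 4: sensitivity to rounding.** The printed 14.2% is 14.215% rounded. If it is read strictly as 14.200%, 27 events just fail (P(X ≤ 27) at 14.2% is 0.0254, above 0.025) and 26 or fewer are needed. At a true 10%, P(X ≤ 26) = 0.470, so the stated outcome then fails in 53% of trials per group.

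**Step 5: what 270 per group delivers with usual assurance at a true 10%.**

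| Events at most | Upper limit at that count | Probability at true 10% |
|---|---|---|
| 27 | 14.2% | 0.551 |
| 31 | 15.9% | 0.821 |
| 33 | 16.7% | 0.904 |

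**Step 6: several groups.** If the true rate were 10% in each of the three investigational groups, all three would have 27 or fewer events with probability 0.551³ = 0.167.

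**The case against.** The best defence is that this is planning shorthand for expected precision. On that reading the number is right even at a true 10%: averaging the exact upper limit over Binomial(270, 0.10) gives 14.198%, and both the mean and the median count are 27. The sentence directly follows a table labelled by observed rates and points back to it, so a careful reader can see which row is meant. That explains where the figure came from, but it does not support the wording. An expected limit of 14.2% is not an assurance that rates above 14.2% are excluded, and the section uses a true rate in its strict sense in its two other statements.

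A second objection is that the 55/45 split depends on rounding (step 4). That is correct, and about 47% to 55% is the full range. The 55% used here is the reading more favourable to the protocol.

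A third is that nothing depends on the sentence. This stands in full. Section 9.1 says "The primary objective of the study will be evaluated descriptively". The planned outputs for Grade 3 solicited events "will be tabulated, per dose and over the whole vaccination course, with exact 95% CI", computed from observed data. The Step 1 holding rules rest on 12 participants per group and their own thresholds, and the 270 per group is not derived from this sentence. These facts limit the severity; they do not make the sentence true.

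**Conclusion.** The concern holds, as a minor one. The sentence treats an observed rate as a true rate and states as certain an outcome that occurs with probability about 0.55 per group when the true rate is 10% (0.47 if 14.2% is read to the last digit). The calculation assumes 270 exposed participants in the group, independent participants and the exact method named in Table 17. The figures printed in 9.2.1 are themselves correct; the fault is in what the 14.2% is conditioned on. Table 17, the sample size, the holding rules and the planned analyses are unaffected.

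**What to change.** Reword the last sentence of protocol 9.2.1. The simplest form is: if the observed Grade 3 AE rate is 10% (27/270), a true incidence above 14.2% is excluded with 97.5% confidence, 14.2% being the upper limit of the two-sided 95% exact interval.

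If a statement about a true rate is preferred, attach its probability: at a true rate of 10%, the upper limit will be at or below 14.2% (14.215% unrounded, 27 or fewer events) with probability about 55%. A more useful planning figure at the same true rate would be an upper limit of 15.9% or lower with probability about 82%, or 16.7% or lower with about 90%.

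The cost is one sentence at the next amendment, or a clarification in the clinical study report. Table 17, the sample size, the holding rules and the SAP stay as they are.

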9.2.2. Statistical Considerations on Immunogenicity Assessment

All the immunogenicity objectives in the study will be evaluated descriptively.

Considering a 20% rate of non-evaluable participants, it is assumed that approximately 864 evaluable participants (216 participants in each group) will be available for the evaluation of the primary immunogenicity objective.

9.2.2.1. Exploratory Immunologic Non-Inferiority Analyses

Exploratory immunologic non-inferiority analyses will be performed in the study, to help in decision making of the formulation selection for phase 3 (Table 18).

The estimated sample size of 216 evaluable participants in each group provides at least 94% power to evaluate non-inferiority of a formulation in terms of antibody geometric mean concentrations (GMCs) measured by the electrochemiluminescence (ECL) assay.

In order to control the global type I error to below 7.5%, Bonferroni correction will be applied. The non-inferiority of each of the investigational formulations will be assessed at 2.5% type I error. That is, the non-inferiority in terms of antibody GMC for the investigational formulation will be reached, if the lower limit of the 2-sided 95% CI for the antibody GMC ratio (investigational group/*Gardasil 9* group) is not less than 0.5 for each of the 9 HPV types. To account for the multiplicity of comparison for 9 HPV types, the global type II errors are conservatively estimated as the sum of individual type II errors.

Table 18 Power to Show That the Lower Limit of the 2-sided 95% CI on Anti-HPV IgG Antibody GMC ratio (HPV-9 Vaccine Group Divided by *Gardasil 9* Group), 1 Month After Dose 3 is Not Less Than 0.5

Standard deviation (Log ₁₀ [concentration])	N evaluable (in each group)	Type II error for each HPV type	Overall Power
0.7	216	0.6%	94.6%

CI = confidence interval; GMC = geometric mean concentration; HPV = human papillomavirus virus; IgG = immunoglobulin G

Power was obtained using PASS 2019, non-inferiority test for 2 means, under the alternative of equal means and variances.

Since there are no immunogenicity data generated with the assay that will be used in this study, several studies with various multivalent HPV formulations in the age group 16-26 years were reviewed and a conservative standard deviation for log₁₀ transformed antibody concentrations of 0.7 for each of the 9 HPV types is used for the computation of power.

If the standard deviation for \log_{10} transformed antibody concentrations is ≤ 0.47 , the sample size of 216 evaluable participants in each group provides at least 73% power to assess the non-inferiority of a formulation in terms of antibody GMCs with a non-inferiority margin of 0.67.

The study also evaluates the **immune responses using a neutralization assay** as a secondary endpoint. If the standard deviation for log₁₀ transformed antibody titers is around 0.6 as observed in HPV-019 (109823) study assessing GSK's bivalent HPV-16/18 AS04-adjuvanted vaccine:

- the sample size of at least 150 participants to obtain 120 evaluable participants at Month 7 provides at least 74% power to assess the non-inferiority of a formulation to *Gardasil 9* in terms of neutralizing antibody geometric mean titers (GMTs) with a non-inferiority margin of 0.5.
- the sample size of at least 270 participants to obtain 216 evaluable participants provides at least 98% power to show the non-inferiority of a formulation to *Gardasil 9* in terms of neutralizing antibody GMTs with a non-inferiority margin of 0.5.

However, note that this does not take into account the multiplicity due to comparisons performed for antibody concentrations measured by ECL assay.

